2. Investigate the impact of role concordance in the treatment decision making process on short term and long term quality of life and decision outcomes. **We hypothesize that:**
 - a. Patients who achieve role concordance will be more satisfied with the decision process.
 - b. Patients who achieve role concordance will have better QOL and less decision regret at early (2 to 6 weeks) and later (6 months) timepoints after the clinic visit.
 - c. Patients who achieve concordance will be more likely to complete or plan to complete recommended treatments.

Study Subjects: The study population will be newly diagnosed female breast cancer patients scheduled to see one of four breast surgeons at the Huntsman Cancer Hospital Breast Surgery Clinic at the University of Utah. We will exclude patients who have had breast cancer previously, cannot read or write, or have a primary language other than English.

Recruitment: All newly diagnosed patients scheduled in our clinic will be given a recruitment letter as part of their new patient materials (sent the day they scheduled their appointment). They will then be called the day before their visit to gauge interest in participation. If they express interest, they will be sent a consent form electronically so that they can familiarize themselves with the study. They will be asked to arrive at least 30 minutes early for their scheduled appointment (most patients do this anyway) and will be met by a research assistant who will explain the study again and obtain written consent. This same assistant will administer the study scales before and after the clinic visit. Providers will not consent patients nor administer any patient assessments for the study because they will also be delivering the intervention. We expect to enroll a total of 100 patients with 50 in the first year and 50 in the second. We see over 400 new breast cancer patients per year and therefore need approximately 12% of these patients per year to participate in order to reach our recruitment goals. Prior studies using similar methods have had excellent enrollment rates with 98% of eligible patients interested in enrollment.

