Data Management: All surveys will be administered electronically (tablets will be used for in clinic surveys) and stored on a secure University server. The surveys will be collected both in person (when the patient is in clinic) and electronically. The surveys will be built into and collected in the Research Subject Registry (RSR) database. Only study personnel will have access to the data and the PI will be responsible for deciding the role and level of access for each person. All digital audio recordings will be stored on a secure, password protected University computer in a locked office at Huntsman Cancer Institute. Again, only study personnel will have access to this data. The digital recordings will be transcribed and de-identified for coding and analysis. The de-identified transcripts will only be available to trained coders, the PI, and study coordinator. The electronic transcriptions will be stored on University based, password protected computers in the secured office area of the PI. Badge access is required to enter the office area during non-business hours. Paper versions will only be used if necessary due to computer outages or significant feasibility issues with the electronic transcripts and will be stored in a locked filing cabinet in the PIs locked office. Again, access will only be given to study personnel.

Statistical Analysis:

We are interested in evaluating whether patients play their desired role in treatment planning, and whether informing providers of patients' preferred roles improves patients' perception of achieving their desired role. Specifically, we will study two groups of patients, a non-intervention control group, where providers are blind to the patient's preferred decision making role and an intervention group where the provider is informed of the patient's preferred role. For this study we plan to enroll 100 patients, where the first 50 will be in the no intervention group and the next 50 will be in the intervention group. We expect the results to provide preliminary data for powering a larger extramural grant.

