The primary aim of our study (a) is to evaluate patient perception of whether the patient achieved his/her preferred role in the treatment decision. This aim will be met by estimating perception concordance between baseline and after the clinic visit within the intervention and control groups, and testing for group differences in concordance. A secondary goal (b) will be to similarly estimate concordance of provider's perception of the patient's preferred role versus the patient's perception of the achieved role (where both scales will be measured after the clinic visit). In addition, we also plan to test the following outcomes between groups: c) patient's satisfaction with the decision making process, d) FACT-B assessment of short-term QOL, e) decision regret, f) OPTION assessment of patient involvement and g) completion or intention to complete therapies. Finally, we will compare the patient role concordance estimated in a) with improved short-term and longer-term improvements in: outcomes c)-g). Specific methods corresponding to each analysis objective are described below.

a-b) Concordance measures. The patient and provider perception scales consist of 5 levels ranging from active to passive involvement in treatment decisions. Consistent with other similar studies [5-7], our primary concordance measure will be defined as exact agreement in patient responses between the baseline and post clinic visit. Within each group we will provide concordance rates and the associated 95% confidence interval (CI) using the Wilson Score interval approach. We will also report the weighted Kappa coefficient and its 95% CI. Group differences in concordance will be tested using a chi-squared or Fisher's exact test. As a sensitivity analysis for this assessment, we may adjust for potential confounders in a logistic framework predicting concordance. We will consider the following variables for adjustment if they are associated with the concordance outcome: age, education level, and stage of disease.

c) Patient's satisfaction with the decision making process. Satisfaction with the decision making process will be measured directly after the clinic encounter using a modified version of the Holmes-Rovner Satisfaction with

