Decision scale which combines several elements of decisional satisfaction and is designed to measure satisfaction with the decision regardless of prognosis or outcome [5, 8]. It also correlates with decision confidence. It uses a Likert-type ranking of 6 items related to the decision. The modified version will measure the satisfaction with the process of decision making rather than the decision itself. Group satisfaction differences will be assessed using a two-sample two-tailed t-test. We will also use linear regression to consider adjusting for the potential confounders described above (a-b) along with the following treatment related variables: type of surgery received and the sequencing of treatment (chemo first vs. surgery first), surgical complications, recommendation for chemotherapy, and recommendation for radiation treatment in these analyses. We will also compare satisfaction with concordance within groups using t-tests (or regression to adjust for covariates). Finally, we will test whether the relationship between satisfaction and concordance differs across groups using linear regression and testing for significance of a group*concordance interaction.

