d) Comparing FACT-B assessment of short-term QOL between the groups. Quality of life will be assessed using the Functional Assessment of Cancer Therapy-Breast (FACT-B) questionnaire. This scale will be used prior to the first consultation to establish a baseline for each patient and will subsequently be used at 2 to 6 weeks and 6 months after initial clinic visit. This questionnaire is a well validated tool for assessing quality of life in breast cancer patients. It measures 27 items in five different areas: physical well-being, social/family well-being, emotional well-being, functional well-being, and additional concerns specific to this patient population. It has been shown to have significant sensitivity for changes in performance status and quality of life [9]. We will compare the FACT-B assessment between the intervention and control groups using a linear mixed effects model framework with an unstructured covariance, adjusting for baseline FACT-B levels. The final time point (6 months) is our main time point of interest, but we will also estimate differences at 2 to 6 weeks. We will consider controlling for the covariates described in c). We will also compare FACT-B with concordance within groups using separate linear mixed effects models for each group. Finally, we will test whether the relationship between satisfaction and concordance differs across groups using linear mixed effects regression and testing for significance of a group*concordance interaction.

e) Decision regret. The decision regret outcome will be measured using the Decision Regret Scale which will also be administered at 2 to 6 weeks and 6 months after initial clinic visit. This scale has been used in modified version to assess for elements specific to breast cancer surgery and was found to have high internal consistency [4]. It is a 5 item scale with items ranked on a 5-point Likert-type scale and added together with higher score indicating more regret. The analysis framework for comparing groups will be similar to d), except that there is no baseline level to control for in the models.

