f) OPTION assessment of patient involvement. The outcome of patient involvement at the clinic encounter will be measured using the OPTION scale. This scale was developed to measure the extent to which providers involve patients in decisions. A description of the measures used and timeline is illustrated in Table 2. With this scale, 2 independent raters will use a 12 item list to code and score a clinical consultation. It provides a reliable method for detecting differences between the extent of patient involvement with good inter-rater reliability and inter-rater agreement [10, 11]. Raters will be hired graduate students who will be trained in this method, with each rater coding and scoring the first 10 transcripts followed by comparison of the results using the intraclass correlation coefficient (ICC) and its 95% CI before switching to a single rater per transcript method. These scores will be compared between the intervention and control groups for differences in patient involvement using a two-sample t-test and linear regression to adjust for the covariates described in c). We will also compare patient involvement with concordance within groups using t-tests (or regression to adjust for covariates). Finally, we will test whether the relationship between involvement and concordance differs across groups using linear regression and testing for significance of a group*concordance interaction.

g) *Completion or intention to complete therapies.* Group differences in completion or intention to complete recommended therapies will be assessed at 6 months after the clinic visit through chart review of all participants' charts. Intent will be defined as initiation or scheduled initiation of a recommended treatment. The variables of decision made (i.e. type of surgery or sequence of therapy) and completion or intention to complete recommended therapies will be compared between groups using a chi-squared or Fisher's exact test. We will also use a logistic regression framework to test whether the relationship between concordance with completion differs by group. We will consider adjusting for a few covariates described in c), keeping in mind a minimum of 5-10 events per predictor in our models. [12]

Table 2.

Measure Name	Assesses	Prior to Clinic Visit	Immediately After Clinic Visit	2 to 6 Weeks After Clinic Visit	6 Months After Clinic Visit
Patient Preference Scale	Patient's preferred role in decision making process	X			

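### Hypothesis 2c has no stated test: section g) tests only whether the concordance-completion relationship differs by group, and section e) states no concordance analysis for regret

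*Combined protocol and SAP*

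**What the plan says.** Objective 2 has three hypotheses, each comparing concordant with non-concordant patients and none restricted to a study group:

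- 2a: "Patients who achieve role concordance will be more satisfied with the decision process".
- 2b: "Patients who achieve role concordance will have better QOL and less decision regret at early (2 to 6 weeks) and later (6 months) timepoints".
- 2c: "Patients who achieve concordance will be more likely to complete or plan to complete recommended treatments".

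The Statistical Analysis overview says that "we will compare the patient role concordance estimated in a) with improved short-term and longer-term improvements in: outcomes c)-g". It then refers the reader to the lettered sections for the method. Those sections provide the following.

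- **c) Satisfaction:** "We will also compare satisfaction with concordance within groups using t-tests (or regression to adjust for covariates", plus a test of the group-by-concordance interaction.
- **d) FACT-B:** "We will also compare FACT-B with concordance within groups using separate linear mixed effects models for each group", plus an interaction test whose sentence names satisfaction as the outcome instead of FACT-B.
- **e) Decision regret:** takes over from d) the approach for comparing the two study groups, minus the baseline term. Concordance is not mentioned.
- **g) Completion:** a chi-squared or Fisher's exact test between study groups, and then "We will also use a logistic regression framework to test whether the relationship between concordance with completion differs by group". Covariates are limited by a minimum of 5 to 10 events per predictor.

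**The concern.** Hypothesis 2c is a claim about a main effect: concordant patients complete more often. Of the two analyses in g), the between-group test does not involve concordance, and the logistic analysis asks only whether the concordance association is different in the two groups. Unlike c) and d), g) does not even give a within-group concordance comparison. A null interaction could be misread as no association between concordance and completion, although it is exactly what a strong association common to both groups would produce.

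For regret the gap is smaller. The overview shows that a concordance comparison is intended, but e) as worded carries over only the group comparison, so the method is missing.

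**Working it through.** **What each test examines.** Write the model as logit P(completion) = b0 + b1·group + b2·concordance + b3·group·concordance. Hypothesis 2c concerns the concordance effect: b2 in a model without the product term. Section g) tests b3 = 0. If the odds ratio is the same in both groups, b3 is exactly zero whatever b2 is, so the test in g) rejects at about its nominal level. The interaction model does contain a b2, but the plan does not say it will be tested, and with 0/1 coding it describes the reference group only.

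**The plan's own figure.** The only power statement (Sample Size Justification) concerns Objective 1: 80% power for a 28-point increase in concordance with 50 per group, two-sided Fisher's exact test at 0.05. From the 50% reference rate, exact enumeration gives 78.9%, which agrees. No power is claimed for Objective 2.

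**Inputs for the illustration.** Concordance is taken as 50% in control and 50 + 28 = 78% in intervention. These are the plan's reference rate and detectable increase, used as assumptions.

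- Control: 50 × 0.50 = 25 concordant, 25 discordant.
- Intervention: 50 × 0.78 = 39 concordant, 11 discordant.
- Total: 64 concordant, 36 discordant.

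Completion rates are not in the documents, so a range is shown. Within each row the rates are the same in both groups. Expected non-completions = 36 × (1 − discordant rate) + 64 × (1 − concordant rate); for example, at 70/90%, 36 × 0.30 + 64 × 0.10 = 10.8 + 6.4 = 17.2. Tests are likelihood-ratio tests at two-sided 5%.

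| Assumed completion, discordant/concordant | Odds ratio | Expected non-completions | Chance of fewer than 10 | Group-adjusted concordance test: power | Interaction test in g): rejection |
|---|---|---|---|---|---|
| 50/90% | 9.0 | 24.4 | under 1% | 99% | 6-8% |
| 60/85% | 3.78 | 24.0 | under 1% | about 76% | 6-8% |
| 70/90% | 3.86 | 17.2 | 1% | 67-69% | 6-8% |
| 80/95% | 4.75 | 10.4 | 39% | 60-62% | 6-8% |
| 85/95% | 3.35 | 8.6 | about 65% | 37% | 6-8% |
| 90/97% | 3.59 | 5.5 | about 95% | 30-32% | 6-8% |

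With 50% concordance in both groups, the concordance test has 83% power at 60/85% and 75% at 70/90%; the interaction test rejects 6% and 8% of the time.

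**Event limit.** At 5 to 10 events per predictor, the interaction model (three predictors) needs 15 to 30 non-completions and the two-predictor model 10 to 20. Fewer than 15 occur with probability 23% at 70/90% and 91% at 80/95%, so the model in g) can itself fall below the limit. When completion is unrelated to concordance (rates of 70 to 95%), the ordinary likelihood-ratio test of concordance rejects 5-7% of the time. Firth's penalised likelihood, used whenever there are fewer than 20 non-completions, brings this to 3-5%, with power of 76%, 66% and 58% at 60/85%, 70/90% and 80/95%.

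**Satisfaction and FACT-B (precision only).** For a single complete measurement, the variances of the concordance difference, in squared SD units, are:

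- control: 1/25 + 1/25 = 0.0800;
- intervention: 1/39 + 1/11 = 0.1166;
- all patients, group-adjusted: 1/(1/0.0800 + 1/0.1166) = 0.0474;
- interaction: 0.0800 + 0.1166 = 0.1966.

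By the noncentral t distribution, the differences detectable with 80% power are 0.81, 0.98, 0.62 and 1.25 SD respectively.

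**The case against.** The best defence is that the overview does commit to relating concordance to all of c) to g), so a reader might wrongly infer that the plan ignores Objective 2. It does not: the intent is stated, and what is missing is the method for completion and regret. For regret, the pattern in c) and d) makes d)'s concordance models the natural reading of e). That part is mostly missing detail, and nothing in the documents says that the test would be picked after seeing the data.

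A reader might also infer that satisfaction and FACT-B get nothing beyond within-group estimates. The documents do not support this. Section c) names t-tests or regression, which test 2a within each group; d) fits a model per group; both add an interaction test. Analysing by group is defensible because the intervention is meant to change concordance. A pooled estimate buys precision by assuming a common association, which the interaction checks only weakly (about 1.25 SD detectable). The study is also presented as preliminary: "We expect the results to provide preliminary data for powering a larger extramural grant".

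Three further points stand. Quality of life, regret and completion are secondary under Outcomes. A scheduled start of treatment counts as intent in g), so non-completion may be rare, and the main-effect test then has little power too. The event limit is worded around adding covariates and does not fix a single threshold.

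None of this supplies a test of 2c. The statement in g) remains an interaction test only.

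**Conclusion.** The point holds for g), and in a weaker form for e). As written, the only concordance analysis of completion rejects about 6-8% of the time under an association common to both groups, so it cannot stand in for a test of 2c. That conclusion does not depend on the assumed completion rates. The gain from adding the right test does: power ranges from about 76% at 60/85% down to 30-32% at 90/97%, so a reader should not infer that the corrected test would be well powered. For regret, the concordance analysis is intended but unspecified. For satisfaction and FACT-B there is no error; a pooled estimate is a matter of precision. This should be changed, though it does not touch the primary concordance comparison.

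**What to change.** 1. **Section g).** State that 2c is tested by the concordance coefficient, with its confidence interval, from a logistic model with concordance and group on all patients. Report it as an association, because concordance is not assigned. Keep the group-by-concordance interaction as secondary. Name in advance a penalised-likelihood or exact method for use if non-completions fall below the events-per-predictor minimum, and fix one figure for that minimum (for two predictors the plan's range gives 10 to 20).
2. **Section e).** State that d)'s concordance models also apply to regret, without the baseline term.
3. **Optional, for precision.** Beside the planned within-group and interaction analyses, add a group-adjusted all-patient concordance estimate for satisfaction and FACT-B.
4. **Minor.** In d), the interaction sentence should name FACT-B.

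The cost is SAP wording and one extra model for completion; no new data or visits are needed. The all-patient coefficient assumes the same association in both groups, which the interaction can check only weakly. If Firth's method is triggered below 20 non-completions, it costs 0 to 4 points of power against ordinary logistic regression in the first three scenarios from 60/85% to 80/95%.

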I prefer that my doctor make the final decision about which treatment will be used but seriously consider my opinion.	My doctor made the final decision about which treatment would be used but seriously considered my opinion.	I made the final decision about which treatment the patient would receive after seriously considering the patient's opinion.
I prefer to leave all decisions regarding my treatment to my doctor.	My doctor made all the decisions regarding my treatment.	I made the final decision about which treatment the patient would receive.

Recording of clinical consultations has been well-studied as a tool for determining patient-centered communication [1-3]. Therefore, all clinic encounters will be digitally recorded, transcribed, and analyzed using the OPTION scale for patient involvement, which is described below. The transcriptions will be de-identified and coded by independent raters (paid graduate students).

Assessments of QOL and decision regret will be performed at early (2 to 6 weeks) and later (6 months) timepoints after the clinic visit. These scales will be distributed electronically and patients will receive a phone call from the study coordinator to remind them to complete the measures. If they have not completed the measures by one week from the reminder phone call, a second call will be placed with an offer to complete the surveys over the phone with the study coordinator.

Chart review of all participants will be reviewed at the 6 month time point to assess for decisions ultimately made and completion or intention to complete recommended therapies. This timeframe was selected because the majority of patients will have completed their surgery, chemotherapy (if needed), and radiation (if needed) or at least have the initiation of these therapies planned. Radiation is always given last and this therapy is the most likely to still be in the planning stages. Also at this time point, endocrine therapy will have been initiated by some patients and may be planned by others.

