Patient Perception Scale	Role the patient perceives they played in decision making process		X		
Provider Perception Scale	Role the provider perceives the patient played in the decision making process		X		
FACT-B	Breast cancer specific health related quality of life	X		X	X
Decision Process Satisfaction Scale	Level of satisfaction patient had with the decision making process		X		
Decision Regret Scale	Regret about decision made			X	X
OPTION Scale	3rd party assessment of patient involvement in decision making (from recorded encounter)		X		

Sample Size Justification

Concordance estimates. A similar study conducted by Bilodeau and Degner estimated 50% agreement between a patient's initial decision-role preference and the role that was achieved [13]. Within each group (n=50), we expect to achieve a confidence interval (CI) width of 29% for an expected concordance of 50%, corresponding to a 95% CI of 36%-64%.

Comparison of intervention versus control concordance. With 50 subjects per group we would have 80% power to detect an absolute increase in concordance of 28% in the intervention versus the control group using a two-sided Fisher's exact test at a 0.05 significance level.

Selected References

1. Hack, T.F., et al., *Behind closed doors: systematic analysis of breast cancer consultation communication and predictors of satisfaction with communication.* Psychooncology, 2010. **19**(6): p. 626-36.
2. Clayton, M.F., et al., *Assessing patient-centered communication in a family practice setting: how do we measure it, and whose opinion matters?* Patient Educ Couns, 2011. **84**(3): p. 294-302.
3. Hack, T.F., et al., *Promoting consultation recording practice in oncology: identification of critical implementation factors and determination of patient benefit.* Psychooncology, 2013. **22**(6): p. 1273-82.
4. Martinez, K.A., et al., *Decision Regret following Treatment for Localized Breast Cancer: Is Regret Stable Over Time?* Med Decis Making, 2015. **35**(4): p. 446-57.
5. Lantz, P.M., et al., *Satisfaction with surgery outcomes and the decision process in a population-based sample of women with breast cancer.* Health Serv Res, 2005. **40**(3): p. 745-67.
6. Janz, N.K., et al., *Patient-physician concordance: preferences, perceptions, and factors influencing the breast cancer surgical decision.* J Clin Oncol, 2004. **22**(15): p. 3091-8.

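### The group-by-concordance logistic model for completion needs at least 15 non-completers under the plan's own events rule, and if completion is about 90% or more, plain maximum likelihood often gives no finite interaction estimate

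*Combined protocol and SAP*

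**What the plan says.** In the combined protocol and SAP, item g of the Statistical Analysis section compares completion between groups by a chi-squared or Fisher's exact test. It then adds a model: "We will also use a logistic regression framework to test whether the relationship between concordance with completion differs by group". Covariates are optional ("We will consider adjusting for a few covariates described in c"), subject to "keeping in mind a minimum of 5-10 events per predictor in our models".

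The outcome is broad, because planned therapy counts as well as completed therapy: "Intent will be defined as initiation or scheduled initiation of a recommended treatment". The Methodology section justifies the 6-month chart review by expecting that by then "the majority of patients will have completed their surgery, chemotherapy (if needed), and radiation (if needed"), or will at least have the start of these therapies planned.

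On size, "the first 50 will be in the no intervention group and the next 50 will be in the intervention group". The Sample Size Justification covers concordance only. It starts from a study that "estimated 50% agreement between a patient's initial decision-role preference and the role that was achieved" and states 80% power for a 28-point increase. The documents give no expected completion rate and no expected number of non-completers. They do not count the predictors in the completion model, and they do not say what happens to the interaction test if events are few or a cell is empty.

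**The concern.** The events rule stands in the sentence on covariates, but the model to which covariates would be added already contains three predictors. The plan does not check whether that base model meets the rule. Limiting covariates cannot remove the interaction term, which the plan says it will test.

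There is also a separate numerical problem. Group, concordance and their product describe four cells with four parameters, so the model is saturated. Its interaction coefficient is a contrast of the four cell log odds. If any cell holds only completers or only non-completers, one of those log odds is infinite and the interaction has no finite maximum-likelihood estimate. Software may still print a coefficient and a standard error, but both depend on when the iterations stop. The team would then choose a remedy after seeing the data, or report an uninterpretable result in a study meant to supply preliminary data for a larger grant.

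**Working it through.** **The plan's own figure.** The documents state no figure for the completion model. The nearest is 80% power for 50% versus 78% concordance, with 50 per group and a two-sided Fisher's exact test at 0.05. Full enumeration gives 78.9%, close to the stated value. It is used here only to set cell sizes.

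**Inputs.**
- N = 100, 50 per group (Statistical Analysis).
- Rule: 5 to 10 events per predictor (item g).
- Control concordance 50%, so 25 concordant and 25 discordant (Sample Size Justification).
- Intervention concordance either 50% (no effect, cells 25/25/25/25) or 50% + 28 points = 78% (0.78 × 50 = 39 concordant, 11 discordant, cells 25/25/11/39). The 78% is the detectable alternative, not a forecast.
- Completion rate q: assumed, 80% to 95%, with non-completion as the rarer outcome.

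**Events rule.** Three predictors × 5 = 15 non-completers; × 10 = 30. Completion must be at most 1 − 15/100 = 85%, or 1 − 30/100 = 70%. Each added covariate parameter needs 5 to 10 more events. Expected events per predictor are 100(1 − q)/3.

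**No finite estimate.** For a cell of m patients, the chance that it holds both outcomes is 1 − q^m − (1 − q)^m. The chance of no finite interaction estimate is 1 minus the product of these over the four cells. Example at q = 0.90 with cells 25/25/11/39: 0.90^25 = 0.0718, 0.90^11 = 0.3138 and 0.90^39 = 0.0164, and the (1 − q)^m terms are negligible. Then 1 − 0.9282 × 0.9282 × 0.6862 × 0.9836 = 0.419.

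| Completion (assumed) | Expected non-completers | Events per predictor | P(at least 15 non-completers) | No finite estimate, 25/25/25/25 | No finite estimate, 25/25/11/39 |
|---|---|---|---|---|---|
| 80% | 20 | 6.7 | 92.0% | 1.5% | 9.3% |
| 85% | 15 | 5.0 | 54.3% | 6.7% | 19.7% |
| 90% | 10 | 3.3 | 7.3% | 25.8% | 41.9% |
| 95% | 5 | 1.7 | 0.01% | 72.7% | 80.5% |

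**Sensitivity.** Letting the cell sizes vary at random changes little: 27.6% and 44.1% at 90% completion, 73.9% and 81.4% at 95%. If completion is 95% in concordant and 85% in discordant patients, the chance is about 49% in either layout. With exactly 15 non-completers it is still 3.6% (equal cells) or 16.8% (25/25/11/39), so meeting the events rule does not by itself prevent the problem.

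**What software does.** In a fit with no non-completers in the cell of 11, the interaction coefficient went from −9.8 to −19.8 to −29.8 as the iterations rose from 10 to 20 to 30. Its standard error rose from 59 to about 1.3 million.

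**The case against.** The strongest reply has four parts.

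1. The events rule refers to the plan's models in general, so it can be read as covering the interaction model and already warning the analyst when that model is too large. This stands, but a warning does not say what to do instead, and the rule does not rule out an empty cell.

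2. The plan names neither ordinary maximum likelihood nor a Wald test. A reader might infer that it commits to a Wald test that must fail; the documents do not say so, and exact or penalised fitting would also fit the wording. A likelihood-ratio test stays finite with an empty cell: with 5/3/0/4 non-completers in cells 25/25/11/39, chi-square is 2.68 and p = 0.10. It is not a clean rescue, however. In null simulations at 80% to 95% completion, its type I error was generally about 6% to 10% against a nominal 5%, while the Wald test almost never rejected at 95% completion.

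3. The trigger is an assumption. A reader might infer from the Methodology section that completion will exceed 85%. The text speaks only of a majority, which is compatible with 70% to 85%. A reader might also infer that starting any one treatment counts as success. Item g defines intent for a single recommended treatment but names the outcome in the plural, and it does not settle whether every recommended therapy is required. If it is, non-completion would be more common.

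4. The 25/25/11/39 layout is the less favourable one. This also stands, which is why the equal-cell figures are shown beside it.

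**Conclusion.** The concern holds in conditional form. The base model has three predictors and needs 15 to 30 non-completers under the plan's own rule, so completion must be no higher than 85%, or 70% at the upper end. Whether that will be met is unknown, because no completion rate is given. Lack of a finite estimate is frequent only from about 90% completion (25.8% to 41.9% of trials, rising to 72.7% to 80.5% at 95%); at 80% to 85% it is occasional (1.5% to 19.7%). The documents do not support saying that the analysis will fail or that the plan breaks its own rule.

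The figures assume 100 patients with complete chart and concordance data, the same completion rate in all cells, and non-completion as the rarer outcome. Missing data would lower the counts. This is a further analysis within a secondary outcome, so improving it is desirable rather than essential. The primary concordance comparison and the simple group comparison of completion are untouched.

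**What to change.** In item g, state that:
- the group-by-concordance model, and any covariate-adjusted completion model, will be fitted by Firth penalised-likelihood logistic regression, with profile-likelihood intervals and a penalised likelihood-ratio test of the interaction;
- completion will be reported alongside it in the four group-by-concordance cells with Wilson intervals, the interval method already planned for concordance in items a-b;
- with fewer than 15 non-completers, no covariates will be added and the interaction result will be labelled exploratory;
- the chi-squared or Fisher's exact test stays for the simple group comparison.

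The cost is a few SAP sentences and standard software, with no extra patients or data. The small downside is slight shrinkage of the estimates and a weaker interaction claim when events are few.
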